## 8.2 Missing, Unknown, or Partial Dates Imputation

Start Date		Stop Date						
		Complete: yyyyymmdd		Partial: yyyyymm		Partial: yyyy		Missing/ Ongoing
<1 st dose	≥1 st dose	<1 st dose yyyyymm	≥1 st dose yyyyymm	<1 st dose yyyy	≥1 st dose yyyy			
		1	n/a	1	n/a	1	1	
Partial: yyyyymm	= 1 st dose yyyyymm	2	2	2	2	2	2	2
	≠ 1 st dose yyyyymm							
Partial: yyyy	= 1 st dose yyyy	3	1	3	1	n/a	1	1
	≠ 1 st dose yyyy		3		3	3	3	3
Missing		4	1	4	1	4	1	1

1 = Impute as the date of first dose

2 = Impute as the first of the month

3 = Impute as January 1 of the year

4 = Impute as January 1 of the stop year

Note: If the start date imputation leads to a start date that is after the stop date, then there is a data error and the start date is not imputed.

Sponsor: Bristol-Myers Squibb

Protocol No.: MB130-069

#### Imputation rules for partial or missing stop dates:

1. Initial imputation
  - a. For partial stop date "mmyyyy", impute the last of the month.
  - b. For partial stop date "yyyy", impute December 31 of the year.
  - c. For completely missing stop date, do not impute.
2. If the stop date imputation leads to a stop date that is after the death date, then impute the stop date as the death date.
3. If the stop date imputation leads to a stop date that is before the start date, then there is a data error and the stop date is not imputed.

#### Imputation rules for partial or missing death dates:

1. If death year and month are available but day is missing:
  - a. If "mmyyyy" for last contact date = "mmyyyy" for death date, set death date to the day after the last contact date.
  - b. If "mmyyyy" for last contact date < "mmyyyy" for death date, set death date to the first day of the death month.
  - c. If "mmyyyy" for last contact date > "mmyyyy" for death date, data error and do not impute.

If both month and day are missing for death date or a death date is totally missing, set death date to the day after the last contact date.

### 8.3 Visit Windows

Visit windows as defined in the protocol are closely monitored by clinical monitors. A protocol deviation will be documented if assessments were recorded outside the visit windows, but the assessment is recorded in the clinical database at the planned visit. For longitudinal summaries of data, assessment recorded at the planned visits in the clinical database are included and displayed in tables with visit based structure.

If there are multiple records within the same visit window, then the value in the visit window closest to the day of the planned visit is selected.

### 8.4 Treatment-Emergent Adverse Events

Treatment-emergent adverse events (TEAEs) are those that first occur or increase in severity or relationship to study treatment after the first dose of study treatment and not more than 30 days after the last dose of study treatment. All AEs that change in severity or relationship to study treatment are assigned a new start date and captured as a new record.

The definitions of AE and SAE can be found in the Protocol [Appendix 9](#). If an AE causality or severity, seriousness or relationship to IP is missing, they will not be imputed.

### 8.5 Adverse Events of Special Interest

A list of adverse events of special interest (AESI) for BMS-986036 based on the known biologic class effects, the mechanism of action, and clinical study data are:

- Injection site reactions
- Gastrointestinal events
  - Diarrhea, frequent bowel movements, nausea, vomiting, abdominal pain
- Bone-related events

Osteoporosis, osteopenia, bone and joint injuries, fractures (except tooth fracture), endocrine abnormalities of gonadal function not elsewhere classified (NEC), hyperparathyroid disorders, hypoparathyroid disorders, parathyroid disorders NEC, parathyroid analyses, metabolic bone disorders, vitamin D abnormal, vitamin D decreased, vitamin D deficiency, and miscellaneous events related to bone density

Sponsor: Bristol-Myers Squibb

Protocol No.: MB130-069

## 8.6 Liver Biopsy Scoring

Histological assessment of the liver tissue sample will be conducted by a blinded Central Pathologist. The central reader will be a medical doctor, board certified in pathology, with experience in liver pathology in a clinical study setting. Additional details on the acquisition, quality requirements, histological preparation, and shipping of histological samples are in the Central Laboratory Manual and the Central Pathology Manual or Charter.

### Histological Scoring

#### NASH CRN

For associated primary and secondary endpoints, the NASH CRN system will be used to score the histologic samples and results are reported as the NAFLD Activity Score (NAS) and the NASH CRN Fibrosis Score. The NASH CRN system is based on the concept that necroinflammatory lesions and stage of fibrosis should be evaluated separately; it assesses liver biopsies for degree of steatosis (0-3), lobular inflammation (0-3), hepatocellular ballooning (0-2), and fibrosis (0-4).

#### NAS

The 3 categories of steatosis, lobular inflammation, and ballooning scores are added together in an unweighted fashion to determine the NAS, which ranges from 0 to 8 (see below).

Histology Variable	Grade	Score
Steatosis	< 5%	0
	5%-33%	1
	> 33% - 66%	2
	> 66%	3
Lobular Inflammation a	none	0
	< 2	1
	2 - 4	2
	> 4	3
Ballooning	none	0
	few	1
	many	2

NAS = NAFLD Activity Score

a Foci per x200 field

#### Fibrosis

#### NASH CRN Fibrosis

Fibrosis is staged separately from NAS on a 0-4 scale: 0 (none); 1 (perisinusoidal or periportal fibrosis); 2 (perisinusoidal and portal/periportal fibrosis); 3 (bridging fibrosis); 4 (cirrhosis).

#### Ishak

A modified Ishak scoring system will also be used to stage fibrosis in the histologic samples. The Ishak system (0-6 scale) was originally developed to grade portal-based liver fibrosis associated with viral

Sponsor: Bristol-Myers Squibb

Protocol No.: MB130-069

hepatitis. The modified Ishak system has been adapted to stage central-based liver fibrosis associated with NASH, and it also uses a 0-6 scale:

- 0: No fibrosis
- 1: centrilobular pericellular fibrosis
- 2: centrilobular and periportal fibrosis
- 3: bridging fibrosis (few bridges)
- 4: bridging fibrosis (many bridges)
- 5: early or incomplete cirrhosis
- 6: established or advanced cirrhosis

### 8.7 Child-Pugh Turcotte Score

The Child-Pugh Turcotte Score assesses the severity of cirrhosis and has been shown to be an accurate measure across a broad spectrum of liver disease. It employs numerical scores of 5 measures of liver disease: total bilirubin, serum albumin, International Normalized Ratio (INR), ascites, and encephalopathy. The sum of scores from each component is the final score (see below) used for determination of class.

Parameter	Classification	Score
Bilirubin (Total)	< 2 mg/dL (< 34.2 µmol/L)	+1
	2-3 mg/dL (34.2-51.3 µmol/L)	+2
	> 3 mg/dL (> 51.3 µmol/L)	+3
Albumin	> 3.5 g/dL (> 35 g/L)	+1
	2.8-3.5 g/dL (28-35 g/L)	+2
	< 2.8 g/dL (< 28 g/L)	+3
International Normalized Ratio	< 1.7	+1
	1.7-2.2	+2
	> 2.2	+3
Ascites	Absent	+1
	Slight	+2
	Moderate	+3
Encephalopathy	No encephalopathy	+1
	Grade 1-2	+2
	Grade 3-4	+3

Class A: 5 to 6 points (least severe liver disease)

Class B: 7 to 9 points (moderately severe liver disease)

Class C: 10 to 15 points (most severe liver disease)

Sponsor: Bristol-Myers Squibb

Protocol No.: MB130-069

## 8.8 Liver-Related Clinical Outcome Events

Participants will be evaluated for the following liver-related clinical outcome events at each visit from Day 1 through Week 52/PTFU:

- All-cause mortality
- MELD Score  $\geq 15$  (with at least a 2-point increase from Baseline)
- Liver transplant
- Ascites requiring medical intervention
- Hospitalization ( $\geq 24$  hours) for onset of variceal bleed
- Hospitalization ( $\geq 24$  hours) for hepatic encephalopathy
- Hospitalization ( $\geq 24$  hours) for spontaneous bacterial peritonitis
- Hepatocellular Carcinoma (HCC)

Liver-related clinical outcome events will also be reported as AEs/SAEs, as applicable, as per ( Protocol Section 8.5.3.1 and [Appendix 9](#)).

## 8.9 CLDQ-NAFLD Scoring

The CLDQ-NAFLD questionnaire (Protocol [Appendix 7](#)) is a disease-specific quality-of-life instrument for nonalcoholic fatty liver disease and NASH. The CLDQ-NAFLD consists of 36 items in 6 domains: abdominal symptoms, activity, emotional function, fatigue, systemic symptoms, and worry. Each item is on a Likert scale with 1 representing the most impairment and 7 representing the least impairment.

Each domain score is an average of its constituent items, and the overall score is an average of the six domains. Any out-of-range value will be considered missing.

In case of missing values, calculation of the domain scores will only be derived when at least 50% of the items are completed, and the total score will require at least three domains.

Items and domains: Ni refers to score obtained for Question i.

Abdominal symptoms (AS) = Mean of N1+N5+N17

Activity/Energy (AE) = Mean of N7 + N9 + N14 + N30+ N31

Emotion (EM) = Mean of N10 + N12 + N15 + N16 + N19 + N20 + N24 + N26 + N34

Fatigue = Mean of N2 + N4 + N8 + N11 + N13 + N35

Systemic (SY) = Mean of N3 + N6 + N21 + N23 + N27 + N36

Worry (WO) = Mean of N18 + N22 + N25 + N28 + N29 + N32 + N33

Overall = Mean of six domains

## 8.10 EQ-5D-3L Scoring

The EQ-5D-3L questionnaire (Protocol Appendix 7) is a general quality-of-life instrument that consists of 2 components, health state description and evaluation. The health state description component measure mobility, self-care, usual activities, pain/discomfort, and anxiety/depression. Participants will rate their level of impairment in each dimension using a 3-level scale. In the evaluation component, participants evaluate their overall health status using a visual analog scale. Any out-of-range value will be considered missing.

The [REDACTED] programming team will also calculate a United States population-based utility index according to Shaw et al. 2005, using a validated program provided by BMS. The index score will not be generated when responses are missing for one or more of the five dimensions.

Sponsor: Bristol-Myers Squibb  
Protocol No.: MB130-069

## 8.11 SF-36 (Version 2)

The SF-36 (Protocol Appendix 6) is a 36-item instrument. Items are divided into eight concepts plus one health comparison question.

The [REDACTED] programming team will use [REDACTED] software [REDACTED] to score the SF-36.

The raw scale scores are computed by summing item responses within each concept after recoding the individual item if needed.

The eight concepts to be scored are:

**Physical Functioning (PF) (items 3a-3j):** The ten items are coded as 1-3. There is no recoding needed. The lowest possible raw score is 10, the highest is 30 and the range is 20. High score indicates better PF.

**Role-Physical (RP) (items 4a-4d):** The items are coded as 1-5. There is no recoding needed. The lowest possible raw score is 4, the highest is 20 and the range is 16. High score indicates better Role- Physical function.

**Role-Emotional (RE) (items 5a-5c):** The items are coded as 1-5. There is no recoding needed. The lowest possible raw score is 3, the highest is 15 and the range is 12. High score indicates better Role-Emotional function.

**Social Functioning (SF) (items 6, 10):** The items are coded as 1-5. Item 6 is recoded as 5-1. Item 10 does not require recoding value. The lowest possible raw score is 2, the highest is 10 and the range is 8. High score indicates better social functioning.

**Bodily Pain (BP) (items 7 & 8):** This concept requires special coding. Item 7 is coded as 1-6 and is recoded as 6.0, 5.4, 4.2, 3.1, 2.2, 1.0. Item 8 is coded as 1-5 and is recoded as 6-1 if both item 7 and item 8 are answered. If item 7 is not answered, item 8 is recoded as 6.0, 4.75, 3.5, 2.25, 1.0. The lowest possible raw score is 2, the highest is 12 and the range is 10. High score indicates lack of bodily pain.

**Mental Health (MH) (items 9b, 9c, 9d, 9f & 9h):** The items are coded as 1-5. Items 9b, 9c and 9f do not require recoding. Items 9d and 9h are recoded as 5-1. The lowest possible raw score is 5, the highest is 25 and the range is 20. High score indicates better mental health.

**Vitality (VT) (items 9a, 9e, 9g, 9i):** The items are coded as 1-5. Items 9a and 9e are recoded as 5-1. Items 9g and 9i do not require recoding. The lowest possible raw score is 4, the highest is 20, the range is 16. High score indicates more vitality.

**General Health (GH) (items 1, 11a-11d):** The items are coded as 1-5. Items 11 a and 11 c do not require recoding. Items 11b and 11d are recoded as 5-1. Item 1 is recoded as 5.0, 4.4, 3.4, 2.0, 1.0. The lowest possible raw score is 5, the highest is 25 and the range is 20. High score indicates better general health perceptions.

**Reported Health Transition (HT) (item 2).** Item 2 is coded as 1-5 and is recoded 5-1.

Any out-of-range value will be considered missing.

Missing or blank values will be estimated using the average recoded score for each concept.

The formula for the transformed scale = [(actual raw score - lowest possible raw score)/Possible raw score range] x 100. The raw scores will be transformed to a 0 – 100 scale.

In addition to the eight concepts above, the scoring software also provides results for two aggregate scores: Physical Component Summary (PCS) and Mental Component Summary (MCS).

## 8.12 Fibroscan

A minimum of 10 valid readings, with at least a 60% success rate of all measurements taken

Sponsor: Bristol-Myers Squibb

Protocol No.: MB130-069

and an interquartile range of less than or equal to 30% of the median value is required for values to be included in summary tables. All values will be listed.

### 8.13 Other Calculations

- ELF assessment combines hyaluronic acid, procollagen 3 amino terminal peptide, and TIMP-1 (tissue inhibitor of metalloproteinases 1). A proprietary algorithm is used to evaluate each of these markers by immunoassay, to create an ELF Score which is provided by an external vendor.
- FIB4 Score =  $(\text{age [years]} \times \text{AST level [U/L]}) / (\text{platelet count } [\times 10^9/\text{L}] \times \text{square root of ALT [U/L]})$ .
- APRI Score =  $([\text{AST divided by AST Upper Limit of Normal}] / \text{platelet count } [\times 10^9/\text{L}]) \times 100$
- NAFLD Fibrosis Score =  $-1.675 + (0.037 \times \text{age [years]}) + (0.094 \times \text{BMI } [(\text{kg/m}^2)]) + (1.13 \times \text{Impaired Fasting Glucose or diabetes [yes = 1, no = 0]}) + (0.99 \times \text{AST/ALT ratio}) - (0.013 \times \text{platelet count } [\times 10^9/\text{L}]) - (0.66 \times \text{albumin } [\text{g/dL}])$ . Note, the status of impaired fasting glucose or diabetes (yes or no) will be assessed only once at baseline as recorded by the site in the Specific Disease History eCRF page. This value will be used for all subsequent calculations.
- MELD Score =  $(9.57 * \ln[\text{creatinine}]) + (3.78 * \ln[\text{Bilirubin}]) + (11.20 * \ln[\text{INR}]) + 6.43$

Note for FIB4, APRI, NAFLD Fibrosis, and MELD scores that if any one component is missing at a given time point, another non-missing value within an absolute range of 3 days may be used. If there is more than one value that is within 3 days, the closest value after the visit date will be selected. Otherwise, if all components are not available the score will not be calculated at that time point.

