- b) ALT value $> 5 \times$ the upper limit of normal (ULN) as defined by the central laboratory
- c) AST value $> 5 \times$ ULN as defined by the central laboratory
- d) Total bilirubin > 1.5 mg/dL
- e) Serum albumin < 3.5 g/ dL
- f) Platelet count $< 100 \times 10^3/\mu\text{L}$
- g) International normalized ratio (INR) > 1.4 , unless due to therapeutic anticoagulation

[figure not shown]
- h) Fasting plasma glucose < 60 mg/dL (< 3.33 mmol/L) or > 350 mg/dL (> 19.43 mmol/L)
- i) Hemoglobin A1c ≥ 10%
- j) Fasting TGs > 500 mg/dL
- k) Estimated glomerular filtration rate (eGFR) < 30 mL/min/1.73 m² according to the Modification of Diet in Renal Disease equation
- l) Evidence of significant worsening of ALT, AST or bilirubin during the Screening Period, in the opinion of the investigator or medical monitor
- m) A centrally read DXA BMD T-Score of -2.5 or less at the femoral neck, total hip, or lumbar spine during Screening (exclusionary only if participant is 40 years of age or older)

[figure not shown]
6. Allergies and adverse drug reactions

- a) History of allergy to FGF21, PEG, or related compounds
- b) History of drug-induced liver injury (DILI)

7. Other exclusion criteria

- a) Prisoners or participants who are involuntarily incarcerated. **Note:** Under certain specific circumstances, a person who has been imprisoned may be included or permitted to continue as a participant. Strict conditions apply, and sponsor approval is required
- b) Participants who are compulsorily detained for treatment of either a psychiatric or physical (e.g., infectious disease) illness
- c) Any factor that, in the opinion of the investigator, would jeopardize the evaluation or safety of the participant or be associated with poor adherence to the protocol
- d) Participants who are incapable of completing study-related assessments (i.e., participant questionnaires) as they MUST be completed by the participant

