8.5.1.8 MELD Scoring

MELD scoring (see [Appendix 10](#)) is a formula for assessing the severity of chronic liver disease that does not include subjective variables such as ascites and encephalopathy. It employs the participant's bilirubin, serum creatinine, and INR.

Blood samples will be taken for bilirubin, serum creatinine, and prothrombin time as part of the hematology and serum chemistry assessments conducted at each visit. The same laboratory will be used for each evaluation. The central laboratory will calculate the MELD Score based on the laboratory values and communicate the score to the site. MELD Scores will be determined at each visit through Week 52/PTFU.

All components of the MELD score should be completed on the same day. If any individual component needs to be repeated on another day, all other components must be repeated as well.

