Appendix 10 Formulae for Measurements

- MELD Score = $(9.57 * \ln[\text{creatinine}]) + (3.78 * \ln[\text{Bilirubin}]) + (11.20 * \ln[\text{INR}]) + 6.43$
- ELF assay combines hyaluronic acid, procollagen 3 amino terminal peptide, and tissue inhibitor of metalloproteinase 1. An algorithm is used to evaluate each of these markers by immunoassay, to create an ELF Score.
- FIB4 score = $(\text{age} [\text{years}] \times \text{AST level} [\text{U/L}]) / (\text{platelet count} [\times 10^9/\text{L}] \times \text{square root of ALT} [\text{U/L}])$
- APRI score = $([\text{AST divided by AST Upper Limit of Normal}] / \text{platelet count} [\times 10^9/\text{L}]) \times 100$
- NAFLD Fibrosis Score = $-1.675 + 0.037 \times \text{age} (\text{years}) + 0.094 \times \text{BMI} (\text{kg}/\text{m}^2) + 1.13 \times \text{fasting glucose/diabetes (yes = 1, no = 0)} + 0.99 \times \text{AST/ALT ratio} - 0.013 \times \text{platelet count} - 0.66 \times \text{albumin} (\text{g/dL})$

[figure not shown]
Method of BMI Calculation:

- Use actual height and weight collected on the same day. Whenever possible, body weight should be measured using the same scale throughout the study.
- To calculate BMI:
 - Convert weight pounds to kg (kg = pounds/2.2)
 - Convert height inches to centimeters (cm = inches \times 2.54)
 - $\text{BMI} = (\text{weight in kg}) / (\text{height in cm}/100)^2$
 - Round to 1 decimal place (if 0.05 or greater, round up)

Appendix 11 Decision Tree for Long-Term Immunogenicity Follow-Up Visits After the Week 52/PTFU Visit

Participants who discontinue study medication prior to Week 48 are expected to complete an ET Visit and to remain in the study and continue to have immunogenicity monitored according to the Schedule of Events in Section 1.

Participants who discontinue study participation will be offered immunogenicity follow-up visits, as per the diagram. All participants will have immunogenicity samples collected at 6 months after the Week 52/PTFU Visit. Additional immunogenicity follow-up visits may occur approximately 9, 12, and 14 months, if applicable, (visit window \pm 14 days) (1 month is defined as 4 calendar weeks) after the last completed study visit.

FU = Follow-Up; IMG = Immunogenicity (anti-drug and anti-FGF21 antibodies); Mo = month (defined as 4 calendar weeks)

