- Noninvasive scores of hepatic fibrosis (AST-Platelet Ratio Index (APRI), Fibrosis 4 (FIB-4), Enhanced Liver Fibrosis (ELF), and NAFLD Fibrosis Score) at Week 24 and Week 48
  - Absolute, percent change, and change from baseline
  - Proportion of participants in each ELF category by time point

Sponsor: Bristol-Myers Squibb

Protocol No.: MB130-069

- Metabolic assessments at Week 24 and Week 48
  - Physical assessments (body weight, waist circumference, and body mass index (BMI)) by time point
  - Serum lipids (low-density lipoprotein (LDL), high-density lipoprotein (HDL), and triglycerides (TGs))
    - Absolute and change from baseline
    - Abnormal postbaseline TG values according to thresholds identified in SAP [Section 4.3.5](#)
  - Plasma glucose, Plasma insulin, Hemoglobin A1c
    - Absolute and change from baseline
    - Abnormal postbaseline glucose values according to thresholds identified in SAP [Section 4.3.5](#)
- Child-Pugh Turcotte Score at Week 24 and Week 48
  - Proportion of participants in each Child-Pugh Turcotte class (A, B, C) by time point
  - Shift from baseline according to class (A, B, C)
- MELD Score at each visit through Week 52/PTFU
  - Absolute and change from baseline
- The event rate for any one (first occurrence) of the liver-related clinical outcome events by Week 48
  - Proportion of participants experiencing any of the events by Week 48
  - Proportion of participants experiencing each liver-related clinical outcome event by Week 48
- Patient-reported outcomes at Week 24 and Week 48
  - 3-Level EuroQol 5 Dimension (EQ-5D-3L) Questionnaire
    - Absolute and change from baseline in visual analog score and utility index
    - Proportion of participants in each 3-level dimension by time point
  - 36-Question Short Form Quality-of-Life (SF-36) Questionnaire
    - Absolute and change from baseline in continuous variables described in SAP [Section 8.0](#)
  - Chronic Liver Disease Questionnaire-Nonalcoholic Fatty Liver Disease (CDLQ-NAFLD)
    - Absolute and change from baseline in continuous variables described in SAP [Section 8.0](#)
- Exploratory biomarkers
  - Transaminases
    - ALT normalization (ALT  $\leq$  ULN) at Week 24 and Week 48
    - AST normalization (AST  $\leq$  ULN) at Week 24 and Week 48
    - ALT at each visit through Week 52/PTFU
    - AST at each visit through Week 52/PTFU
    - Change from Baseline (Day 1 predose) ALT levels at each visit through Week 52/PTFU Visit

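### SAP 8.13 computes MELD without a lower bound on its inputs or stated units, so a low creatinine can keep a Child-Pugh A-to-B deterioration below the MELD ≥ 15 event threshold

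*SAP*

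**What the plan says.** SAP 8.13 gives MELD as "9.57 * \ln[\text{creatinine}]) + (3.78 * \ln[\text{Bilirubin}]) + (11.20 * \ln[\text{INR}]) + 6.43". Protocol Appendix 10 ("Formulae for Measurements") prints the same expression. Neither place sets a minimum for any component or names the units of creatinine and bilirubin, although SAP 8.13 does give units for inputs such as AST, platelet count and albumin in the neighbouring scores.

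The only handling rule attached to the SAP formula concerns missing data: "if any one component is missing at a given time point, another non-missing value within an absolute range of 3 days may be used". The imputation rule in SAP 6.2.4 deals with limits of quantification in laboratory summary tables, so it does not act as a floor for MELD.

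The score is used twice in SAP 4.5, both times as an exploratory endpoint:
- "MELD Score at each visit through Week 52/PTFU", summarised as absolute value and change from baseline.
- As part of the liver-event rate, including "Proportion of participants experiencing each liver-related clinical outcome event by Week 48". SAP 8.8 lists eight such events. One is a MELD score of 15 or more "with at least a 2-point increase from Baseline".

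Protocol 8.5.1.8 adds a second source for the score: "The central laboratory will calculate the MELD Score based on the laboratory values and communicate the score to the site".

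**The concern.** The logarithm of a value below 1.0 is negative. Used raw, a creatinine, bilirubin or INR below 1.0 does not merely add nothing; it takes points away from whatever the other two components contribute. Creatinine has a coefficient of 9.57 and is the main driver here.

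Two things are at stake. First, the absolute score can fall below the constant 6.43 and even below zero, and shifts of creatinine within a low range move it by several points. Second, the event uses a fixed threshold of 15. Two participants with identical bilirubin and INR can be classified differently because one has a creatinine of 0.7 and the other 1.0.

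There is also a consistency risk. If the central laboratory applies bounds that the SAP does not, the score known to the site and the analysed score can disagree on whether an event occurred. The documents do not say which score feeds the endpoint.

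**Working it through.** The documents give no worked MELD value, so there is no figure to reproduce. The check evaluates the printed formula directly.

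**Inputs**
- Formula: SAP 8.13 and protocol Appendix 10, with natural logs. Creatinine (Cr) and bilirubin (Bili) are assumed to be in mg/dL.
- Eligibility, protocol 8.3.2: the bilirubin exclusion is "Total bilirubin > 1.5 mg/dL"; INR above 1.4 is excluded unless due to therapeutic anticoagulation; eGFR below 30 is excluded. None of these prevents low creatinine, bilirubin or INR.
- Event rule: SAP 8.8. Yardstick for deterioration: Child-Pugh table, SAP 8.7.
- The creatinine values are assumed and shown as a range, because the documents give no distribution.

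**Step 1: a low eligible baseline.** Cr 0.6, Bili 0.5, INR 1.0:

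9.57 ln(0.6) + 3.78 ln(0.5) + 11.20 ln(1.0) + 6.43 = -4.89 - 2.62 + 0 + 6.43 = **-1.08**

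At INR 1.0 the score is negative only when creatinine is below these values:

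| Bilirubin (mg/dL) | Creatinine below (mg/dL) |
|---|---|
| 0.3 | 0.82 |
| 0.4 | 0.73 |
| 0.5 | 0.67 |
| 0.7 | 0.59 |
| 1.0 | 0.51 |

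Cr 0.8, Bili 0.5, INR 1.0 gives +1.67, so not every low profile is negative.

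**Step 2: creatinine alone.** 9.57 ln(Cr) is -1.01 at 0.9, -2.14 at 0.8, -3.41 at 0.7 and -4.89 at 0.6. A move from 0.6 to 0.8 adds 9.57 ln(0.8/0.6) = 2.75 points. That exceeds the 2-point rise in the event rule but is not an event unless the score also reaches 15.

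**Step 3: a defined deterioration.** Bilirubin 3.0 and INR 1.7 each score 2 in SAP 8.7. With 1 point for each of the other three items the total is 7 (class B), up from 5 (class A). The bilirubin, INR and constant terms give 3.78 ln(3.0) + 11.20 ln(1.7) + 6.43 = 4.15 + 5.94 + 6.43 = 16.53. Adding the creatinine term:

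| Creatinine | MELD as printed | Reaches 15? |
|---|---|---|
| 0.6 | 11.64 | no |
| 0.7 | 13.11 | no |
| 0.8 | 14.39 | no |
| 0.9 | 15.52 | yes |
| 1.0 | 16.53 | yes |

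A participant going from the Step 1 baseline to the first row rises 11.64 - (-1.08) = 12.7 points and records no MELD event.

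**Step 4: how far the threshold moves.** At INR 1.7, the bilirubin needed to reach 15 is exp[(15 - 6.43 - 5.94 - 9.57 ln Cr)/3.78]: 2.0 mg/dL at Cr 1.0, 3.5 at 0.8, 4.9 at 0.7 and 7.3 at 0.6.

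**Step 5: with inputs floored at 1.0 (assumed).** The minimum score is 6.43. Every row of the Step 3 table becomes 16.53. The rise from the Step 1 baseline becomes 16.53 - 6.43 = 10.1 points instead of 12.7, and the 0.6-to-0.8 creatinine move becomes 0.

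**Step 6: units.** SAP 6.2.4 reports laboratory results in both SI and US units. The Step 1 profile in µmol/L (factors 88.4 for creatinine, 17.1 for bilirubin) gives 9.57 ln(53.04) + 3.78 ln(8.55) + 6.43 = 52.5 instead of -1.08.

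**The case against.** The strongest case against is that this is a minor clarification. Several parts of it stand.

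- **The floor is not in the documents.** Nothing names 1.0, so every floored figure above is conditional on that choice.
- **Prevalence is unknown.** A reader might infer that eligible participants in general will score below zero. The documents do not support that: a negative score needs low creatinine together with low bilirubin and an INR near 1. Upper limits at entry permit low values but do not show how common they are, and the eGFR limit admits higher creatinine too.
- **Mean change.** A reader might infer that mean MELD change mostly reflects creatinine noise. No variance or distribution is given to support this. A stable low creatinine cancels in a difference, and creatinine belongs in MELD by design.
- **The floor has a cost.** It helps the threshold but shortens change from baseline (Step 5).
- **Consequence is limited.** Both endpoints are exploratory, and MELD ≥ 15 is one of eight event types. The Step 3 patient would also appear in the Child-Pugh class shift if the values were present at Week 24 or Week 48. The same formula applies to every blinded arm, so nothing points to a between-arm bias.
- **The laboratory may already apply bounds** in a manual that is not part of these documents.

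These points narrow the claim without removing it. The formula as printed, followed exactly, classifies identical bilirubin and INR differently according to low-range creatinine, and no other section corrects this.

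**Conclusion.** The point holds in a limited form and merits a SAP change. Assuming mg/dL, the printed derivation lets some eligible participants have negative scores. It also fails to count a Child-Pugh A-to-B deterioration (bilirubin 3.0, INR 1.7) as a MELD event at creatinine 0.6 to 0.8, while counting it at 0.9 and above.

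The affected band is bounded on both sides. At bilirubin 2.0 and INR 1.7 the score is 14.99 even at creatinine 1.0, so a floor changes nothing. At bilirubin 4.0 and INR 2.2 the score is 15.61 even at creatinine 0.6, so the event counts either way.

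The effect is confined to the exploratory MELD score and liver-event composite; the primary and secondary histology endpoints are untouched. How many participants would change event status cannot be derived from the documents. That no bound or unit is printed is certain; the effect on the trial's results is not.

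**What to change.** Change the SAP derivation only (8.13):

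1. State that creatinine and total bilirubin enter in mg/dL.
2. Set creatinine, total bilirubin and INR values below 1.0 to 1.0 before taking logs. Label the floor as an assumption, chosen because each log term is zero at 1.0.
3. Use this one derivation for baseline, change from baseline and the MELD ≥ 15 event.
4. Confirm with the central laboratory which units and bounds its score uses (protocol 8.5.1.8, Appendix 10), reconcile the two, and state which score is analysed. Any departure from Appendix 10 can be recorded in SAP 2.5.

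Leave the protocol formula as it is. Protocol 8.5.1.9 ties a liver-related event to contact with the medical monitor about further participation, and an analysis convention should not alter that.

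The cost is one line of SAP text, one line of code on data already held, and a query to the laboratory. The statistical downside is that change from baseline is compressed where inputs lie below 1.0. Listing participants whose event status differs with and without the floor would show how much it matters.
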